22.1.3. During the Hotel Period in the Study Period

Auto Mode Evaluation:

- Time in different range (% of i-STAT): BG < 50, 54, 60, 70 mg/dL, 70 mg/dL ≤ BG ≤ 180 mg/dL, BG > 180, 250 mg/dL
- Number of Events, AUC and Time in the hyperglycemic range: i-STAT® glucose > 180, 250, 350 mg/dL
- Number of Events, AUC and Time in the hypoglycemic range: i-STAT® glucose < 50, 54, 60, and 70 mg/dL

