Subjects 2-6 years of age are not required to participate in a hotel study. Instead, they will participate in an out-of-home study for 5 consecutive days, 4-6 hours per day. During that 5 day period, subjects should engage in significant activity/exercise. Such activities could include utilizing gym play areas appropriate for toddlers and young children, swimming, and playground games. Evidence of geographic location and exercise/activity will be documented by daily photograph. In addition, investigational center staff will be present daily for the 4-6 hours of exercise during the 5 day period.

Auto Mode Frequent Sample testing

While in Auto Mode, subjects 7-13 years of age will undergo daytime and/or nighttime Frequent Sample Testing (FST) during the Hotel study with i-STAT® used as a reference value.

Subjects 7-13 years:

Overnight frequent sample testing (10PM to 7AM) in Auto Mode will be every 30 minutes; daytime frequent sample testing (7AM to 10PM) in Auto Mode will be every 60 minutes. The exact times of FST may differ, but the interval for testing should remain as described.

Subjects 2-6 years:

During one of the days of the out-of-home study subjects should undergo frequent sample testing for 4-6 hours using SMBG as a reference method. The frequent sample testing period will be supervised by investigational center staff. Frequency of testing is every 30 minutes. .

Note 1: The Auto Mode Frequent Sample Testing may be performed at any time during the hotel study (7-13 years) or the out-of-home study (2-6 years).

Note 2: It is important that calculation of total blood draw be maintained throughout the study so that the total amount of blood volume does not exceed the maximum each subject is allowed. If the maximum is reached, FST will be stopped.

All participating investigational centers will target 3-6 subjects (7-13 years) to undergo a hotel study on Day 7 to Day 14 in Month 1 of the study period. On Days 1-6 of the Study period, during which data necessary for Auto Mode initiation is collected, subjects will not be permitted to turn Auto Mode ON. Entry into Auto Mode will occur on day 7 whether at home or in hotel. A minimum of 4 subjects are recommended to participate in each of the hotel studies. However, the sponsor has discretion to allow more or less subjects to attend a hotel stay should the site request this.

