- Failure to obtain informed consent prior to performing one or more study procedures.
- Failure to maintain ICFs on file for all subjects who have provided informed consent.
- Use of an ICF that has not received approval from the IRB/EC.

- Use of an incorrect version of the ICF.

- 11. **Study Visits – Enrollment and Run-In Period**
- 11.1. **Run-in Period Synopsis**

Run-In Period Synopsis (Visit 1-4)

The primary purpose of the run-in period is to allow study subjects to become familiar with the study devices and to assure they meet criteria for study participation. Subjects will also be asked to undergo overnight frequent sample testing to evaluate the *Low Management Suspend before Low* feature of the study pump at Run-in Visit 4. There is a window of 90 days from the end of Visit 1 to Visit 4 during which time subjects should complete run-in. If the run-in period is repeated an additional 30 days will be added to the run-in period window. If a repeat of the *Low Management Suspend before Low* testing is necessary, Sponsor discretion will be used to determine timing of the repeat.

Success criteria for run-in:

- Subject must have 3 or greater than 3 SMBG per day
- Subject must show sensor compliance (i.e. 2,880 glucose sensor data points equivalent to 10 days of sensor wear)
- Subject does **not** turn on the SmartGuard Low Management features before the *Low Management Suspend before Low* Frequent Sample Testing at Run-in visit 4
- Subject does **not** turn on the Auto Mode feature

The run-in period should be repeated if the subject does not meet all run-in success criteria as listed above or if the Investigator believes the subject needs to gain greater familiarity with study devices.

Subject should be withdrawn if they turn on the Auto Mode feature during this period.

• **Devices Worn:**

- Subjects are trained on all study devices prior to receiving them
- Subjects 2-13 years of age: Sensor is inserted by subject or with assistance from parent(s)/guardian(s)/companion(s) into either the abdomen or buttocks and connected to GST3C Transmitter

• **Calibration Requirements with Study Meter:**

- Approximately 30 minutes to 2 hours after the Sensor is initialized, the Study Pump will alert the user to enter meter BGs to perform initial calibration
- After the first calibration, the user must calibrate the Sensor within 6 hours of the first calibration
- The user must calibrate when prompted by the study pump via the Smart Cal feature

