11.5.5. Hotel Study (All subjects who are participating in a Hotel/Clinic study)

Overview

- Cohorts
 - Hotel Study Month 1 (Day 7 – Day 14)
 - Hotel Study Month 2 (Day 36 – Day 66)

- Hotel Study Month 3 (Day 67 – Day 96)
- **Duration:** 6 days
- **Location:** Hotel, House or clinic
- **Goal:** Activities in the mornings and afternoons
- **Safety:** All study Safety Criteria apply to hotel study equally.
- **Activity Plan (Exercise and other activities):**
 - Subjects will not be forced or coerced to complete activities if they do not feel they are capable to complete them. Activity intensity may be adjusted so that subjects are able complete the activity.
 - Site research staff will record subject activities, including the types of activity and the time they are performed.
 - Information on subject activity will be collected in eCRF.
 - There will be numerous activity periods throughout each day for a minimum of approximately 4 hour minimum - 6 hours maximum in total per day. It is understood that exercise/activity on the days subjects are doing FST may be limited. For example, subject would not be able to go swimming with IV in their arm. Activity choices may include the following but not limited to:
 - Walking including walking up and down stair case or hiking
 - Shopping
 - Swimming – such as water aerobics, playing in water, water volleyball, marco polo
 - Aerobics
 - Dancing – such as slow dance
 - Any sport activity which involves ongoing physical movement (i.e., tennis, golf, basketball, tee ball or volleyball)
 - Yoga/stretching
 - Biking

Note: Subjects should perform BG check prior to any aerobic exercise and only start to exercise if BG is >120mg/dL.

- **Auto Mode Frequent Sample Testing (i-Stat® reference for subjects 7-13 years of age)**
 - Placement of IV may be performed.
 - Subjects 7-13 years: During one day and one night of the hotel or clinic stay (any day or night may be selected) each subject will undergo FST in Auto Mode.
 - Night time Auto Mode FST will be between 10PM and 7AM (start no earlier than 8PM)
 - Day time Auto Mode FST will be between 7AM and 10PM (start no earlier than 5AM)

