 - Subjects 2-6 years: Frequent sample testing in Auto Mode will be required for approximately 4-6 hours during one day of the Out-of Home study, using SMBG as a reference method. The frequent sample testing period will be supervised by investigational center staff. Testing frequency will be every 30 minutes. The exact times of FST may vary, but the interval for testing should be followed as described.
 - Maximum blood draw for all subjects is 2 ml/kg for any 24 hour period and 4 ml/kg over a 1 month period.
 - Subjects 7-13 years: Overnight frequent sample testing in Auto Mode will be required for approximately 24 hours. Nighttime frequent sample testing (10PM to 7AM) in Auto Mode will be every 30 minutes; daytime frequent sample testing (7AM to 10PM) in Auto Mode will

be every 60 minutes. The exact times of FST may differ, but the interval for testing should remain as described. The exact times may be changed, but overnight FST should start no earlier than 8PM and daytime FST should start no earlier than 5AM. Approximately 24 hours of Auto Mode FST (15 daytime hours and 9 nighttime hours) should be performed.

- **Meals:**
 - No specific food intake restrictions for scheduled meals or snacks
 - Subjects may eat breakfast, lunch and dinner on their own
- **Subject Sleep Attire**

Subjects will wear pajamas or clothes which cover torso and undergarments.
- **Research staff monitoring:**
 - **During night** – subjects have fingerstick glucose checks starting at 12AM and again at 3AM
 - At each required time, fingerstick checks for all subjects may take 1-1.5 hours to be completed
 - 1 Medical staff who is able to test SMBG, accompanied by 1 research coordinator
 - Privacy/safety protocols (i.e., knock on door first, identify)
 - **During FST**
 - Every 30- 60 minutes
 - i-STAT® as reference method
 - Additional monitoring by SMBG made be performed based on i-STAT® glucose and management decisions will be made by SMBG in order to reflect actual use
- **Minimum Staffing**
 - MD should be on call as per routine study procedures and attend hotel/house visit for approximately 8 hours throughout the hotel/house stay.
 - One registered nurse, Nurse Practitioner or Physician Assistant for every 2 subjects, on site who is able to test SMBG. This medical professional should have experience in the treatment of hypoglycemia, including severe hypoglycemia with glucagon, hyperglycemia, including severe hyperglycemia and management of ketones and sick day rules.

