22.1. Descriptive Endpoints

22.1.1. During the Home Period

- The mean change in A1C will be presented from baseline to end of study
- Change of Total Daily Dose (TDD) of insulin from baseline to end of study
- Change of weight from baseline to end of study
- Time spent in Auto Mode versus time spent in Manual Mode

- Time in different range (% of SG): SG < 50, 54, 60, 70 mg/dL, 70 mg/dL ≤ SG ≤ 180 mg/dL, SG > 180, 250 mg/dL, 350 mg/dL
- Number of Events, AUC and Time in the hyperglycemic range: sensor glucose (SG) > 180, 250, 350 mg/dL
- Number of Events, AUC and Time in the hypoglycemic range: SG < 50, 54, 60, and 70 mg/dL

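### Hotel time in range (ages 7-13) is labelled a percentage of i-STAT, but night is sampled twice as often as day; if taken as a plain share of values, night gets 54.5% of the weight for 37.5% of the time

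*Protocol*

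**What the plan says.** **Endpoint.** Protocol Section 22.1.3, repeated in Section 24.2 and the synopsis, lists "Time in different range (% of i-STAT" for a set of glucose thresholds. The corresponding home endpoint in Section 22.1.1 is "Time in different range (% of SG". Beside each stand bullets on event counts, AUC and time above or below thresholds.

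**Sampling, ages 7-13.** Section 4 (Study Design) gives "Overnight frequent sample testing (10PM to 7AM) in Auto Mode will be every 30 minutes" and "daytime frequent sample testing (7AM to 10PM) in Auto Mode will be every 60 minutes". It lets clock times vary but keeps the intervals. Section 11.5.5 adds "Approximately 24 hours of Auto Mode FST (15 daytime hours and 9 nighttime hours) should be performed". It also sets earliest starts of 8PM for the night and 5AM for the day.

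**Coverage per subject.** Section 11.5.5 has testing "During one day and one night of the hotel or clinic stay". The synopsis and Section 4 are looser and allow day testing, night testing or both.

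**Sensor data.** Section 11.1 equates "2,880 glucose sensor data points equivalent to 10 days of sensor wear".

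**Timing of the Month 1 hotel study.** The overviews in the synopsis timeline and Section 8.2 put it on Days 1-6. The synopsis design text, Section 4, Section 11.5.5 and the Month 1 cohort schedules (synopsis and Section 8.2) put it on Days 7-14. Section 11.5.1 does not allow Auto Mode during the first 6 days of the study period.

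**The concern.** A percentage of readings equals a percentage of time only when readings are equally spaced. Sensor readings are, so the home label is harmless. Carried over to i-STAT, the same label meets a schedule that takes twice as many samples per hour at night as by day. A plain count would let the sampling plan, not the clock, set the mix of night and day.

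Section 11.2 says the hotel portion compares the system with a reference value both by day and by night. Control may well differ between the two. Section 11.5.5 gives the activity goal as "Activities in the mornings and afternoons" (though activity may be limited on testing days) and leaves eating unrestricted. Equal night and day percentages therefore cannot be presumed. The protocol gives no day or night glucose figures, so the direction of any error is unknown.

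The Day 1-6 conflict is a separate matter. The hotel i-STAT endpoint evaluates Auto Mode, and a stay on Days 1-6 falls wholly within the days when Auto Mode is not permitted.

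**Working it through.** **1. Reproduce the plan's own split.** 10PM to 7AM is 9 hours and 7AM to 10PM is 15 hours; 9 + 15 = 24. This matches Section 11.5.5.

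**2. Sensor spacing.** 2,880 / (10 × 24) = 12 readings per hour, one every 5 minutes. For the sensor, a share of values is a share of time.

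**3. i-STAT values in a complete profile.**
- Night: 9 × 60 / 30 = 18
- Day: 15 × 60 / 60 = 15
- Total: 33

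**4. Night's weight.**
- As a share of values: 18/33 = 54.5%
- As a share of time: 9/24 = 37.5%
- Difference: 0.5455 − 0.3750 = 0.1705

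Counting boundary samples differently changes little: 18/34 = 52.9%, 19/35 = 54.3%, 19/34 = 55.9%.

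**5. Effect on the endpoint.** Let N and D be the night and day percentages at a given threshold.
- Plain share of values: U = (18N + 15D) / 33
- Share of time: T = (9N + 15D) / 24
- U − T = (18/33 − 9/24) × (N − D) = 0.1705 × (N − D)

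**6. Size.** The gaps below are assumptions, since the protocol gives none.

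| Assumed gap, N − D (points) | U − T (points) |
|---|---|
| 0 | 0 |
| ±5 | ±0.9 |
| ±10 | ±1.7 |
| ±20 | ±3.4 |

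Check with N = 80, D = 60: U = (18×80 + 15×60)/33 = 70.9 and T = (9×80 + 15×60)/24 = 67.5, so +3.4. With N = 60, D = 80: U = 69.1 and T = 72.5, so −3.4.

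**7. Subjects with one period only.** Within a single period the interval is constant, so a share of values equals a share of sampled time. That figure describes only that period.

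**8. Ages 2-6.** Testing uses SMBG every 30 minutes throughout, so the weighting question does not arise.

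**9. Month 1 timing.** Days 1-6 (overviews) and Days 7-14 (the other places cited) do not overlap. With Auto Mode barred on Days 1-6, a stay on those days would give no Auto Mode reference data for that cohort.

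**The case against.** The strongest reply is that the protocol never says the values are counted unweighted. The words in brackets may only name the source of the data, to tell i-STAT from sensor. The neighbouring bullets ask for AUC and time, and AUC from samples 30 and 60 minutes apart cannot be computed without using the intervals, so time-based handling is already in view. A statistical analysis plan, not shown here, may settle the computation. All of this stands as a limit on the claim. A reader might infer that the plan has fixed a wrong analysis; the text does not go that far. What remains is that the protocol itself sets both the label and an uneven schedule, and the label's most natural reading does not measure time on that schedule.

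Two further inferences are tempting and not supported:

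- **Movable start times change the split between night and day.** Section 11.5.5 keeps 15 day hours and 9 night hours alongside the earliest starts, and those starts preserve it: 8PM to 5AM is 9 hours and 5AM to 8PM is 15. They describe a shift of the whole schedule.
- **Early stopping makes the imbalance worse.** Testing does stop at the blood-volume limit, but the documents give no i-STAT sample volume. Nothing shows when, or whether, a subject would reach the limit during this testing.

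It is also fair to say that the effect may be nil, and that separate day and night figures are a presentation choice.

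**Conclusion.** The point holds as a minor one. It rests on three conditions: that the endpoint is computed as a plain share of values, that the profile is complete at 9 night and 15 day hours, and that night and day percentages differ. Under the first two, night carries 54.5% of the weight for 37.5% of the time, and the reported percentage is off by 0.170 times the night-minus-day difference. Without the third the error is zero.

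The reach is one untested descriptive endpoint in ages 7-13. A1C, the sensor-based tests, the sample size and ages 2-6 are unaffected. Because the wording on coverage differs between Section 4 and Section 11.5.5, some subjects may contribute only one of the two periods.

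The Day 1-6 versus Day 7-14 conflict is a plain contradiction that stands on its own. It neither supports nor depends on the weighting point.

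**What to change.** - In Sections 22.1.3 and 24.2 and the synopsis, define the hotel endpoint as a percentage of sampled time. Weight each i-STAT value by the interval it represents, taken from recorded sample times, and use the same basis for the neighbouring AUC and time bullets.
- Optionally, show day and night percentages separately, so that a subject with one period sampled contributes to that period only.
- Align the wording on day and night coverage in the synopsis and Section 4 with that in Section 11.5.5.
- Separately, reconcile the Day 1-6 statements (synopsis overview, Section 8.2 overview) with the Day 7-14 statements and the restriction in Section 11.5.1.

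The weighting change costs one sentence in three places and simple programming, with no extra samples. Reported percentages may move by a few points either way, or not at all.

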22.2. Exploratory Analysis

22.2.1. Analysis of Primary Endpoint

The primary effectiveness endpoint is change in A1C from baseline to end of 3-month treatment period, defined as A1C measured at the 3-month treatment visit minus A1C measured at the randomization visit. The goal is to show simple superiority in reducing A1C from baseline to end of 3-month study period.

22.2.2. Analysis of Secondary Endpoint

The secondary endpoints are hierarchically ordered and will be evaluated in the fixed sequence from endpoint 1 to 3 during the study phase.

- **Secondary Endpoint: % of Time in Euglycemia (70 – 180 mg/dL)**

The overall mean change in % of time in euglycemia (70-180 mg/dL) from baseline to the end of study will be estimated and compared by a simple superiority paired test and a significance level of 0.025 (one-sided).

- **Secondary Endpoint: % of Time in Hyperglycemia (> 180 mg/dL)**

The overall mean change in % of time in hyperglycemia (> 180 mg/dL) from baseline to the end of study will be estimated and compared by a simple superiority paired test and a significance level of 0.025 (one-sided).

- **Secondary Endpoint: % of Time in Hypoglycemia (< 70 mg/dL)**

The overall mean change in % time in hypoglycemia (< 70 mg/dL) from baseline to the end of study will be estimated and compared by a simple superiority paired test and a significance level of 0.025 (one-sided).

22.3. Safety Data Summarized

- Serious Adverse Events (SAE), Serious Adverse Device Effects (SADE)
- Unanticipated Adverse Device Effects (UADE)
- Incidence of Severe Hypoglycemia
- Incidence of DKA

23. Administrative Considerations

23.1. Study Closure Procedures

Upon completion of the study, when all subjects have completed their visit schedules, all eCRFs have been entered and all related queries have been resolved. The study devices, unused study materials and equipment will be collected and returned to Medtronic and/or its designees (see table 1). Medtronic and/or its designees will notify the investigational center of its intention to close out the study and a close-out visit will be conducted. The Monitor will ensure that the Investigator's regulatory files are up-to-date and complete and that any outstanding issues from previous visits have been resolved. Other issues that will be reviewed at this visit include discussing retention of study files, possibility of investigational center audits, and notifying the IRB/EC of study closure.

23.2. Document Storage and Retention

The Sponsor and Investigator will retain all records and documents pertaining to this study. They will be available for inspection by the appropriate regulatory agencies. In addition, the Investigator will retain the source documents from which the information entered on the eCRF was derived. These records are to be retained in a secure storage facility maintained by the investigational center until 2 years (or longer/shorter if local laws require) after approval of the above-listed study devices or termination of the study, whichever is longer. The Investigator should not dispose of these records without the approval of the Sponsor. The investigator should take measures to prevent accidental or early destruction of the clinical study related materials.

23.3. Data Handling

All data required for analysis will be captured on eCRFs using OC-RDC module. Original eCRFs will not be as source data and supporting documentation will be required. However, in cases where center-administered, web-based subject questionnaires are considered source data, said source data is electronic and associated systems must comply with CRF 21 Part 11 requirements. Electronic device data will be collected from the 670G Pump System using Medtronic CareLink Clinical. The system uses Secure Sockets Layers (SSL) technology, which encrypts all data it stores (21 CFR Part 11 compliant). Certain data points stored in the uploaded information may also be captured on the appropriate eCRF.

The Investigator will ensure that all eCRFs are completed promptly, completely, and accurately. Information on case report forms must conform to the information in the source documents. Medtronic will provide detailed

instructions to assist with eCRF completion. In the event of data discrepancies, investigational centers will be asked to resolve queries electronically in the RDC system; otherwise, irresolvable data-related issues will be routed to the Sponsor for review and final disposition. An audit trail is maintained in OC-RDC to capture any corrections or changes of the eCRFs. If a person is only authorized to complete CRFs or to make changes to an already signed CRF, the investigator shall re-sign this CRF. System backups for data stored in the OC-RDC system will be consistent with Medtronic standard procedures.

Medtronic will only consider eCRFs to be complete when all discrepancies between source data and eCRF have been resolved and eCRF content has been reviewed by a Study Monitor. In addition, specific eCRFs must also be reviewed and electronically signed by the Investigator, indicating his/her agreement with the accuracy of all recorded data. It is expected that the Investigator and his/her staff will cooperate with the monitoring team and provide any missing data in a timely manner.

23.4. Data Preparation

Prior to data extraction, all collected data will undergo a final verification by Data Management. Documentation of this verification will be maintained in the sponsor study files. Upon the completion of the verification, data will be extracted and transferred to the appropriate personnel for analysis.

23.5. Training of Clinical Staff

Training of the investigational center staff on the conduct of the study and system being studied will be initiated before the protocol is implemented. All participating physicians and coordinators will be familiarized with the system. Specific investigational center staff will be trained on each of the system's components. Training will contain both lecture and hands-on experience.

